8.2 POWER ANALYSIS OR STATEMENT OF PRECISION

In a one-way ANOVA, sample sizes of 19 DLB, 38 AD, and 38 CN achieve 80% power to detect differences among the means versus the alternative of equal means using an F test with a 0.01 significance level and assuming a common standard deviation within a group of 0.05. This is true for any set of group means with a standard deviation greater than or equal to 0.02, which we anticipate being able to achieve based on previous research. All significant brain connection couples in Franciotti's work had standard deviations of the group means greater than 0.06.

For post-hoc tests, group sample sizes of 19 DLB, 38 AD, and 38 CN patients achieve 81% power to reject the null hypothesis of equal means when the population mean difference is 0.05 with a standard deviation for both groups of 0.05 and with a significance level (alpha) of 0.010 using a two-sided two-sample equal-variance t-test.

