4.2 OVERVIEW – STUDY PROCEDURES/DATA COLLECTION

Data will be obtained for cognitive measures and imaging data (rs-fMRI, DTI, T1) from ADNI 2/3 data base cohort subjects with AD diagnosis, CN and DLB subjects recruited from a multidisciplinary dementia clinic. See the section # for detailed study procedures/data collection. Cognitive tests were selected so as to be harmonized with those used with the ADNI-2/3 database.

This research investigation will take place at the Center for Memory and Aging at the HealthPartners Neuroscience Center (multidisciplinary dementia clinic). Potential candidates will also be referred to our site through the Park Nicollet Neurology Clinic.

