5 STUDY POPULATION

For ADNI 2/3 data, we will include CN and AD subjects who have undergone rs-fMRI images (with DTI and T1 images) and have cognitive/function testing data available. Below we describe the study population regarding clinic recruitment.

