7.1.4 MRI IMAGING

Subjects will undergo MRI imaging at HealthPartners Neuroscience Center. Subjects will be screened for any contraindications for MRI. Subjects will undergo a protocol based on recommendation by Omniscent (o8t MR Acquisition Recommendations). We anticipate 15 minutes of scan run time using a 3T Siemens Skyra scanner and the following images will be obtained.

- 1) High-resolution multi-scan directional diffusion scan, which is most similar to a diffusion tensor image (DTI) acquisition - Specifically, diffusion weighted imaging with the following acquisition parameters will be used: *2 mm x 2 mm x 2 mm voxels, FOV = 25.6 cm, matrix = 128 mm x 128 mm, slice thickness = 2.0 mm, one non-zero b-value of b = 1000, 40 directions, and gap = 0.0 mm.*

- 2) EPI BOLD rs-fMRI - A resting-state fMRI as a T2-star EPI sequence, with 3 x 3 x 3-mm voxels, 128 volumes/run, a TE = 27ms, a TR = 2.8s, a field of view – 256mm, a flip angle = 90°
- 3) Anatomical Scan –T1 Weighting

All images will be de-identified and uploaded to the infinitome cloud-based server to be analyzed. Internal guidelines/best practices based on infinitome user manual will be developed for transfer, obtaining accounts, uploading of raw images and downloading of analyzed data.

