7.2 ADNI DATABASE

A data use agreement with ADNI will be completed prior to downloading the data for analysis from the ADNI database (ADNI Database). A user login – for research staff will be used for downloading the data.

All necessary ADNI data for MCI, mild AD patients, and cognitively normal (CN) will be downloaded to a local secure server for further analysis.

Data will be obtained regarding demographics, medical history, cognitive assessments (as mentioned in earlier sections), MMSE for eligibility, biomarkers and imaging (as mentioned in the previous section). The imaging data will be uploaded and processed with the Infinitome software as stated in the previous sections.

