8 STATISTICAL CONSIDERATIONS

8.1 STATISTICAL ANALYSIS PLAN

Preliminary data analysis: One-way ANOVA will be used to compare demographic and baseline clinical characteristics across groups. **no missing data expected, SAS, p-value

Aim 1 Analysis: For the between-group analysis of functional connectivity, general linear model multivariate analysis of variance will be used with FC values between pairs of LSBN parcellations as dependent variables and group (DLB, AD, and CN) as a factor variable. Bonferroni post hoc test will be used to correct for multiple comparisons. The primary pairs of interest (see **Table 4**) based on available literature (see background and **Table 2**) will be analyzed first. Other combinations of these seven parcellations will be analyzed secondarily. If additional, unexpected anomalies are present between groups, we will test them in an exploratory fashion to advance this novel field of study.

Aim 2 Analysis: Pearson correlation analyses will be performed between functional connectivity values and neuropsychological test scores to evaluate the relationship between connectivity strengths and the clinical phenotype of DLB. Similar to Aim 1, we will focus on pre-specified pairs of interest, but will explore others if they present themselves in the functional connectivity analysis.

Table 4: Data Variables
Population Descriptors: age, sex, race, ethnicity, education, measures of baseline cognition (e.g. MoCA)
Aim 1: Evaluate the role of rs-fMRI and connectomic analysis as a biomarker of disease in DLB using data from an ADNI-2/3 population of MCI and mild AD subjects and a clinic population of DLB subjects
Group variable: DLB, AD, or CN

Dependent variables: Functional connectivity (FC) scores between pairs of LSBN parcellations
 
 • Primary pairs of interest (see background for justification of these choices): 
 ○ Locus coeruleus v. Basal nucleus of Meynert ○ Locus coeruleus v. Intralaminar nucleus of thalamus ○ Basal nucleus of Meynert v. Intralaminar nucleus of thalamus ○ PH v. FST ○ Substantia nigra v. Caudate nucleus • Exploratory pairs: Other 15 combinations of the pre-specified parcellations, other pairs of parcellations found to be anomalies by Infinitome program
Aim 2: Correlate cross-sectional dysfunction between LSBN parcellations with specific neuropsychological abnormalities in DLB Patients

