06 FEB 2024

Aim 1

Our primary aim was to evaluate the role of rs-fMRI and connectomic analysis as a diagnostic imaging biomarker of disease for LSBN deterioration in DLB by comparing a clinical population of DLB patients with the ADNI 2/3 cohort of CN and AD/CI subjects. Specifically, we compared FC scores of prespecified parcellation pairs between the three groups using a one-way ANOVA. Eight parcellation pairs were chosen as the primary pairs, and twenty-two as the exploratory pairs.

Aim 2

Our secondary aim (aim 2) was to correlate cross-sectional dysfunction between LSBN parcellations with specific neuropsychological abnormalities in DLB patients. To accomplish this, we performed a two-stage analysis. First, we compared cognitive test scores between groups to understand which successfully distinguished between the cohorts. When possible, test scores were normed, i.e., converted to a Z- or T-score adjusted for age, sex, and years of education.

Primary Comparisons/A Priori Hypotheses:

- 1) *ADAS Number Cancellation Targets will be lower in DLB patients*
- 2) *Trails B time will be higher in DLB patients*
- 3) *Clock Drawing Tests will be lower in DLB patients*
- 4) *ADAS construction praxis score will be lower in DLB patients*
- 5) *Category Fluency Animals will be lower in AD patients*
- 6) *RAVLT recognition will be lower in AD patients*

The remaining comparisons were exploratory: Trails A time, RAVLT immediate recall, RAVLT delayed recall, Functional Activities Questionnaire (FAQ), Logical Memory Immediate, and Logical Memory Delayed. Digit Span Forward, Digit Span Backward, and Boston Naming Test were either missing or highly incomplete in ADNI controls; therefore, they were described in the DLB cohort only.

In the second part of the Aim 2 analysis, we correlated test scores with FC scores from the primary parcellation group in Aim 1, within diagnosis (DLB, CN, or AD/CI) and compared these correlations across diagnosis group. As above, we prespecified 4 hypotheses to test and consider the remaining correlations to be exploratory. Because of the high volume of statistical tests performed in the exploratory analysis, we used the Holm correction to adjust the p-values in the exploratory correlations only.

Primary/ A Priori Hypotheses:

- 1) *Caudate R / Substantia Nigra R and the Clock Drawing Test will be differently correlated for DLB patients vs other groups.*

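### Aim 1 rests on pooled-variance tests across two scan sources and unequal groups, with no basis given for equal SDs; Welch tests would be a cheap safeguard

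*Combined protocol and SAP*

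**What the plan says.** Section 8.2 sizes the study for 19 DLB, 38 AD and 38 CN subjects. The overall F test is powered at the 1% level, "assuming a common standard deviation within a group of 0.05". The post hoc comparisons are powered for a mean difference of 0.05 with SD 0.05 in both groups, "using a two-sided two-sample equal-variance t-test". The only outside support cited there is an earlier rs-fMRI study's spread of group means. That is between-group spread and says nothing about the within-group SD.

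For the analysis, Section 8.1 plans a general linear model MANOVA on the connectivity (FC) scores with group as factor, and "Bonferroni post hoc test will be used to correct for multiple comparisons". The Updated A Priori SAP of 06 FEB 2024, under Aim 1, says "we compared FC scores of prespecified parcellation pairs between the three groups using a one-way ANOVA". Neither mentions an unequal-variance form, a check of spread, or per-group SDs.

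On scan source, Section 7.1.4 puts the DLB subjects through "15 minutes of scan run time using a 3T Siemens Skyra scanner" with listed sequence parameters. For the comparators, Section 5 says "we will include CN and AD subjects who have undergone rs-fMRI images (with DTI and T1 images", which requires the image types but sets no acquisition criteria. Section 4.2 says "Cognitive tests were selected so as to be harmonized with those used with the ADNI-2/3 database"; nothing similar is said about imaging. Section 7.1.5 does send all images through the same tool, and Section 7.2 repeats this for the ADNI images.

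**The concern.** With unequal group sizes, a pooled test keeps its nominal level only if the SDs are equal. Here diagnosis and scan source coincide completely, so equal spread is not something to take for granted. The allocation is 1:2:2, and the group of interest is the smallest.

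DLB supplies 18 of the 92 error degrees of freedom in the ANOVA (20%) and 18 of 55 in a two-sample t-test (33%). Yet even with equal SDs it contributes two thirds of the sampling variance of a DLB contrast: (1/19)/(1/19 + 1/38) = 2/3. If DLB spread differs from ADNI spread, the pooled standard error is therefore wrong for exactly the comparisons that carry the diagnostic-biomarker claim. It is too small if DLB is more variable and too large if DLB is less variable.

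**Working it through.** **Inputs.** From Section 8.2: n = 19/38/38, alpha 0.01, within-group SD 0.05, SD of group means 0.02, post hoc difference 0.05. The ratio r = DLB SD / ADNI SD is not in the documents. It is an assumption, shown from 0.5 to 2 with AD and CN both at SD 0.05.

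**Step 1: the plan's own figures.**
- F test: noncentrality = 95 × 0.02² / 0.05² = 15.2 on 2 and 92 df, using means weighted by n. Power is 82.0% against 80% stated; a value of 0.0195, which rounds to 0.02, gives 79.5%.
- t-test, 19 v 38: noncentrality = 0.05 / (0.05 × √(1/19 + 1/38)) = 3.56 on 55 df. Power is 80.9% against 81% stated.

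Under equal SDs the stated figures stand. The two effects also agree: DLB alone differing by 0.05 gives a weighted SD of means of 0.05 × √(0.2 × 0.8) = 0.02.

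**Step 2: size of the standard-error mismatch.** For the two-sample pooled t-test,

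reported SE / true SE = √[ ((18r² + 37)/55) × (1/19 + 1/38) / (r²/19 + 1/38) ].

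- r = 0.5: 1.23
- r = 1: 1.00
- r = 1.5: 0.88
- r = 2: 0.81

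**Step 3: true type I error and power at nominal 1%.** Simulation with normal data, 200,000 runs per setting. Power is for DLB alone differing by 0.05.

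| r | Type I: pooled F | Type I: pooled t | Power F: pooled / Welch | Power t: pooled / Welch |
|---|---|---|---|---|
| 0.5 | 0.7% | 0.2% | 96% / 99.9% | 95% / 99% |
| 0.67 | 0.7% | 0.4% | 92% / 98% | 92% / 96% |
| 0.8 | 0.8% | 0.6% | 88% / 93% | 88% / 91% |
| 1 | 1.0% | 1.0% | 82% / 79% | 81% / 79% |
| 1.25 | 1.6% | 1.7% | 74% / 58% | 71% / 61% |
| 1.5 | 2.5% | 2.4% | 66% / 41% | 62% / 46% |
| 2 | 4.8% | 3.7% | 53% / 21% | 46% / 26% |

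Welch's ANOVA and the Welch t-test stay at 1.0% to 1.1% type I error in every row. Repeat runs differ by about 0.1 percentage point in type I error. For r above 1, the higher power of the pooled tests is not a like-for-like advantage, because those tests exceed their nominal level.

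**Step 4: another nominal level.** The 2024 SAP states no level for Aim 1. At nominal 5% the pattern is the same: at r = 1.5 the F test has 8.7% and the pooled t 8.6%; at r = 2 they have 12.1% and 11.1%.

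**The case against.** A common SD is an ordinary planning assumption. The words that state it stand in the power section; for the analysis itself, pooling is inferred from the names of the methods. No document shows unequal SDs, so every figure away from r = 1 depends on an assumed ratio. All images pass through one tool. All of this stands, and it limits the point to an unsupported assumption rather than a demonstrated error.

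Three stronger readings are tempting, and the documents do not support them.

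- A reader might infer that Aim 1 false positives are inflated. The direction is unknown. One scanner and one protocol for DLB would, if anything, suggest less spread in DLB. So would a mixed comparator: Section 7.2 says "All necessary ADNI data for MCI, mild AD patients, and cognitively normal (CN) will be downloaded" and the 2024 SAP refers to AD/CI, although Section 5.5 limits the group to mild AD with supportive biomarkers. In that direction the DLB tests are conservative.
- A reader might count expected false positives over 16 contrasts (eight primary pairs, two contrasts each). At r = 1.5 that is 16 × 0.0333 = 0.53 using the three-group error term, or 16 × 0.0237 = 0.38 with the two-sample test of Section 8.2, against 16 × 0.01 = 0.16. But this joins the protocol's 1% level, set when there were five primary pairs, to the SAP's eight pairs, and the SAP names neither an Aim 1 level nor post hoc contrasts.
- A reader might infer that a less variable DLB group would leave the study underpowered. With ADNI spread as planned, pooled power stays above 80%. The loss is only relative to Welch, about 92% v 96% for the t-test at r = 0.67.

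It is also fair to say that complete overlap of diagnosis with scan source threatens mean FC more directly than its spread, and that Welch tests do nothing about that.

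**Conclusion.** The point holds as an unsupported equal-variance assumption in a design that is sensitive to it. The stated power figures are sound if the SDs are equal. If they are not, the pooled tests do not hold their level: over assumed ratios of 0.5 to 2, true type I error at nominal 1% is 0.7% to 4.8% for the F test and 0.2% to 3.7% for the two-sample t-test. They are anti-conservative if DLB is more variable; if it is less variable, they are conservative with a modest loss of power relative to Welch. Whether Aim 1 results would change is unknown until per-group SDs are reported. The figures rest on normal data, the planned group sizes (the 2024 SAP gives none) and equal spread in AD and CN. This is a worthwhile, inexpensive improvement, not a flaw that invalidates the plan.

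**What to change.** - For each primary pair, make Welch's ANOVA and Welch t-tests for DLB v AD and DLB v CN, with the planned Bonferroni adjustment, the main univariate tests.
- Keep the pooled ANOVA and the Section 8.1 MANOVA as sensitivity analyses. Do not choose between pooled and Welch tests by a preliminary variance test.
- Report n, mean and SD of FC per group, with Welch confidence intervals for both DLB contrasts.
- In Section 8.2, label the common SD of 0.05 as an assumption and restate the power.
- The 2024 SAP is written in the past tense, so label the Welch analysis as added later if results had been seen.

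**Cost.** No new patients or scans are needed. With equal SDs, power falls from about 82% to 79% (ANOVA) and from 81% to 79% (t-test), just under the planned 80%. If the DLB SD were 1.5 times the ADNI SD, power at the planned difference of 0.05 under valid tests would be only about 41% (F) and 46% (t), and the restated power section should say so. A shift in mean FC between scan sources remains uncorrected and should be named as a separate limitation.

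### The 81% post-hoc power in section 8.2 includes no correction for the three group contrasts; if the 0.01 level is split over them, power for the DLB contrasts is about 69%

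*Combined protocol and SAP*

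**What the plan says.** Section 8.1 (Aim 1 Analysis) plans a multivariate general linear model on the connectivity values with "group (DLB, AD, and CN) as a factor variable", and adds that a "Bonferroni post hoc test will be used to correct for multiple comparisons". It does not say whether the correction covers the group contrasts, the connection pairs or both, and it gives no family-wise alpha. Table 4 lists five primary pairs.

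Section 8.2 powers the three-group comparison "using an F test with a 0.01 significance level". For the post-hoc tests it says that "group sample sizes of 19 DLB, 38 AD, and 38 CN patients achieve 81% power" "when the population mean difference is 0.05 with a standard deviation for both groups of 0.05", "with a significance level (alpha) of 0.010 using a two-sided two-sample equal-variance t-test". It does not explain where 0.01 comes from.

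The updated SAP of 06 February 2024 changes Aim 1 to a one-way ANOVA and says: "Eight parcellation pairs were chosen as the primary pairs, and twenty-two as the exploratory pairs". It states no alpha and no post-hoc correction for Aim 1. Its only stated multiplicity adjustment, Holm, is limited to the exploratory correlations of Aim 2.

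**The concern.** A Bonferroni post hoc test that follows a three-level group factor would most naturally correct the pairwise group contrasts: DLB v AD, DLB v CN and AD v CN. Section 8.2 uses 0.01 for the F test, before any contrast is made, and the same 0.01 for each contrast afterwards. The quoted power therefore describes a post-hoc test with no correction at the contrast level.

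The two contrasts involving DLB answer the diagnostic question of Aim 1, and they have the least power because DLB is the smallest group. A chance of about 31% of missing the planned difference, where the plan implies 19%, would change how a null DLB v AD result is read. While the family stays undefined, the significance threshold also stays open after the data are seen.

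**Working it through.** **Inputs (section 8.2).** n = 19 DLB and 38 in each comparison group; difference 0.05; common SD 0.05; two-sided equal-variance t-test; alpha 0.010. The number of contrasts (three) follows from the three-level factor in 8.1; the documents do not state it.

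**Method.** Noncentrality δ = Δ / (σ√(1/n₁ + 1/n₂)). Power = P(T > t at 1 − α/2), where T is noncentral t with n₁ + n₂ − 2 degrees of freedom; the opposite tail is negligible.

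- DLB contrasts: δ = 0.05 / (0.05 × √(1/19 + 1/38)) = 3.559, df = 55.
- AD v CN: δ = 0.05 / (0.05 × √(2/38)) = 4.359, df = 74.

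**Step 1: the plan's figure.** At α = 0.010 the critical value is 2.668 (df 55) and power is 80.9%. The stated 81% is reproduced. It belongs to 19 v 38 only; AD v CN at the same level has 95.4%.

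**Step 2: split 0.01 over three contrasts.** α = 0.01/3 = 0.0033, which equals 0.05/15. The critical value rises to 3.069. Power for a DLB contrast is 68.6%; for AD v CN it is 90.3%. At this alpha a difference of 0.055 has 79.6% power and 0.0555 has 80.5%, so the difference detectable with 80% power is about 0.055.

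**Step 3: other readings of the family, DLB contrast.**

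| Reading | Alpha per contrast | Power |
|---|---|---|
| Three contrasts, no correction across pairs | 0.05/3 = 0.0167 | 85.8% |
| Five pairs only, contrasts uncorrected | 0.05/5 = 0.010 | 80.9% |
| Five pairs, two DLB contrasts | 0.01/2 = 0.005 | 73.4% |
| Five pairs, three contrasts | 0.01/3 = 0.0033 | 68.6% |
| Eight pairs only (updated SAP) | 0.05/8 = 0.00625 | 75.9% |
| Eight pairs, three contrasts | 0.05/24 = 0.0021 | 62.8% |

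**Step 4: error if only the five pairs are corrected.** With all three group means equal, three t-tests at 0.01 reject at least once in about 2.7% of simulated data sets per connection. Over five connections, if independent, that is 1 − (1 − 0.027)⁵ = 12.8%. The 5% implied by 0.05/5 is not held.

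**Step 5: pairwise tests at 0.01 only after a significant F test at 0.01.** Both tests must then pass, so power depends on the third group's mean, which the documents do not give. Simulated power for one DLB contrast was:

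- about 77% with AD and CN equal;
- about 73% with the third mean midway between the two compared;
- 72%, the lowest value found, with it two-thirds of the way from DLB to the comparator;
- 81% with it well outside the two.

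**The case against.** The strongest defence is that the documents never specify 0.0033. Reaching it takes three inferences: that 0.01 is 0.05/5, that all three contrasts form a family, and that this family sits inside 0.01. If Bonferroni was meant for the five pairs only, 0.010 is already the corrected level and 81% stands. If it was meant for the three contrasts at 0.05 per connection, 81% is conservative. This part of the defence holds. A reader might infer that 8.2 contains an arithmetic error, or that the plan requires 0.0033 and its true power is 69%. The documents support neither: the 81% follows from its own inputs, and 69% is conditional on one reading of the family.

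The defence does not remove the point. The five-pairs reading leaves the contrasts uncorrected (step 4). The 0.05/3 reading is hard to square with an F test at 0.01. For the eight pairs of the updated SAP, 0.010 is no longer 0.05 over the number of pairs.

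A second defence is that real effects may be larger. Section 8.2 says the significant connections in the study it cites had group means with an SD above 0.06. The configuration least favourable to DLB puts its mean midway between AD and CN. Each DLB contrast is then at least 0.06/√(76/95) = 0.067, with about 95% power even at 0.0033. That is fair as far as it goes. It covers only connections already selected as significant, and outside that configuration it speaks only for the larger of the two DLB contrasts. Section 2.1 describes that study's finding as one on the posterior cingulate, which is in none of the primary pairs listed here.

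Finally, the updated SAP is written in the past tense, so restating power will not alter the sample size. It still governs how null results are read.

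**Conclusion.** The point holds in conditional form. The post-hoc power in 8.2 is computed at the F-test level, with no allowance for the three group contrasts, while 8.1 announces a Bonferroni post hoc test whose family is undefined. On the most natural reading (0.01 per connection, split over three contrasts), power for DLB v AD and DLB v CN is about 69% against the stated 81%. Over all the readings examined it runs from about 63% to 86%. These figures assume a difference of 0.05, SD 0.05 and 19 v 38; that 0.01 comes from 0.05/5 is likely but not stated. AD v CN is much less affected, at about 90% at 0.0033.

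**What to change.** In 8.1 and the updated SAP, state the family, the family-wise alpha and a per-contrast alpha that covers both the primary pairs and the group contrasts. In 8.2, restate the DLB-contrast power at that alpha: about 69% at 0.0033 for five pairs, or about 63% at 0.05/24 for eight. Give AD v CN (38 v 38) on its own line, about 90% at 0.0033.

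Alternatively, replace Bonferroni across the three contrasts by pairwise tests at the per-connection level, done only after a significant F test at that level. With three groups this controls the error rate within each connection. At 0.01 its power is roughly 73% to 81% (72% at the lowest point simulated), so the assumed mean of the third group must be stated with the figure. With eight primary pairs, the per-connection level itself would have to be reset and the power recomputed.

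The cost is one or two sentences in each place and a less favourable stated figure. No extra patients are needed.
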